2.3 Patient disposition, demographics and other baseline characteristics

2.3.1 Patient disposition

Patient disposition will be summarized on RAS. The number and proportion of patients, who complete the study, are ongoing in the study or discontinue the study prematurely along with the primary reason for discontinuation will be presented. Listings will also be provided for primary reason for early discontinuation.

The number of patients in each analysis set described above will also be presented. Reason for screen failure will be summarized for all screened participants.

A listing will present all patients randomized, but not treated.

Randomized

Subjects are considered randomized if they have been assigned a randomization number.

Completing the DBTE

Subjects are defined as completing the DBTE if they complete the week 12 assessment, or if they miss the week 12 assessment, but continue to enter the OLTE. It will be derived from the Double-Blind Treatment Study Completion Form with “Completed” as the reason for ending study epoch.

Completing the Study

Subjects are defined as completing study if they complete the whole 64 weeks of study evaluation.

Exposed to Investigational Product

Subjects are defined as being exposed to IP if they receive at least one dose of IP.

Completing the Double-Blind Investigational Product

Subjects are defined as completing double-blind IP if they complete the week 8 IP dose or temporarily withhold IP at week 8 and continue to receive IP during OLTE.

Completing Open-label Investigational Product

Subjects are defined as completing open-label IP if they complete the week 60 IP dose.

2.3.2 Background and demographic characteristics

Demographic variables and other baseline characteristics including previous migraine treatments will be summarized using descriptive statistics by randomized treatment group and overall study population using the RAS.

At baseline, following demographic and baseline characteristics will be summarized:

- Sex
- Ethnicity
- Race

- Age
- Height (cm)
- Weight (kg)
- Body Mass Index (BMI, kg/m²)
- Acute headache medication (migraine-specific/non migraine-specific) during baseline phase
- Summary of prior migraine prophylactic treatment and reasons for discontinuation
- [REDACTED]
- Age at onset of migraine (years)
- Disease duration of migraine
- Monthly migraine days during baseline phase
- [REDACTED]
- Monthly headache days during baseline phase
- Monthly acute medication use in days during baseline phase

Descriptive statistics (mean, median, standard deviation, minimum, and maximum) will be presented for continuous variables for each treatment group and for all participants (total). The number and percentage of participants in each category will be presented for categorical variables for each treatment group and all participants (total).

2.3.3 Medical History

Relevant medical history/current medical conditions present before signing the Informed consent #1 will be recorded on the ‘Medical History’ CRF page. Only listings will be presented.

Medical history possibly contributing to liver dysfunction will be record separately on the ‘Medical History Possibly Contributing to Liver Dysfunction’ CRF page and presented separately in frequency tables by SOC and PT and in listings.

Any condition entered will be coded using the latest version Medical Dictionary for Regulatory Activities (MedDRA) prior to database lock and summarized by primary system organ class (SOC) and preferred term (PT) for each treatment arm for RAS.

2.4 Treatments (study treatment, rescue medication, concomitant therapies, compliance)

2.4.1 Study treatment / compliance

Subcutaneous (sc) injections are to be given for each investigational product administration. For purposes of study treatment dosing, “qm” refers to an every 4 weeks injection regimen.

Double-Blind Treatment Epoch:

AMG 334 140 mg or placebo will be administered by qualified study staff at the each dosing visit during the 12-week double-blind treatment epoch (ie, at Day 1 and Weeks 4 and 8).

Study medication is administered by the investigator or designated study staff at each visit. This information should be captured in the source document and the eCRF at each visit. All

study treatment dispensed and returned must be recorded in the Drug Accountability Log. Site staff will review eDiary compliance with the patient at each visit.

Compliance:

Compliance to eDairy at each month is calculated as:

1. (Number of observed eDairy days at baseline or between IP doses/ 28)*100% if Number of actual days in Baseline epoch or between IP doses interval ≤ 28 or
2. (Number of observed eDairy days at baseline or between IP doses/ Number of actual days in Baseline epoch or between IP doses interval)*100% if Number of actual days in Baseline epoch or between IP doses interval > 28 .

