5.5.4 Instructions for prescribing and taking study treatment

Subcutaneous (s.c.) injections are to be given for each investigational product administration. For purposes of study treatment dosing, “q.m.” refers to an every 4 weeks injection regimen. The study drug administration date should be in 4 week increments (+/- 5 days) from the first dose of study drug. Any dose administrations that may occur greater than +/- 5 days from the 4 week time point (e.g., patient unavailability) should be discussed with the Sponsor prior to dosing. The anatomical sites for administration of investigational product are the upper arm, upper thigh, or abdomen; the location of the injection sites should be documented in the source document.

Double-Blind Treatment Epoch:

Two injections of AMG 334 70 mg (equaling 140 mg total dose) or placebo will be administered by qualified study staff at each dosing visit during the 12-week double-blind treatment epoch (i.e., at Day 1 and Weeks 4 and 8).

Open-label Treatment Epoch and PTA-Open-Label Treatment Epoch:

Two injections of open-label AMG 334 70 mg (equaling 140 mg total dose) will be administered by qualified study staff at each dosing visit during the 156-week open-label treatment epoch (ie, at Weeks 12, 16, 20, 24, etc.) and during the PTA-Open-Label Treatment Epoch (ie, at Weeks 168, 172, 176, 180 etc.). If and when 140 mg/mL pre-filled syringes become available during the Open-Label Treatment Epoch, the 140 mg dose may be administered by a single 140 mg/mL s.c. injection.

The investigational product dose is fixed and will not be adjusted for individual patients during the study. There are no temporal restrictions for study drug administration (e.g., proximity to meals, sleep or activity).

All kits of study treatment assigned will be recorded in the IRT. Novartis monitors will reconcile treatment assigned vs treatment administered and ensure that the information is congruent during their monitoring visits.

During the **COVID-19 pandemic** that limits or prevents on-site study visits, delivery of study drug directly to a patient’s home is generally permitted in the event the Investigator has decided that an on-site visit by the patient is no longer appropriate or possible, and that it is in the interest of the patient’s health to administer (e.g., self-injection or study staff administration at patients’

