Listings will include all assessments, sorted by scheduled visit and time of assessment, flagging unscheduled visits. The listings will include analysis windows and corresponding flags to indicate the assessment's inclusion in analysis.

Further details regarding analysis windows for specific domains are included in Tables below.

Monthly Interval for Efficacy Endpoints

Monthly efficacy measurements will be calculated based on the subject's monthly investigational product(IP) dosing schedule defined below using eDiary data collected from beginning of the baseline phase (week -4 visit) up to open label treatment period.

Table 2 Study Intervals for Efficacy Endpoints

Study Phase	Assessment Timepoint	Interval Based on Dose Dates	
		Start date	End date
Baseline Epoch	Baseline	From eDiary device assignment date (or Week -4 visit)	Day prior to study day 1
Double-Blind Treatment Epoch	Week 4	Study Day 1	
 • Week 4 dose date-1 • Study day 28 if Week 4 dose is not received (either missed or IP discontinued prior to Week 4) 
Note: if day 1 dose is the last IP dose subject received, the rest of monthly rates during DBTE will be calculated based on consecutive 28-day interval beginning on study day 29 (ie, 29-56 for week 8, 57-84 for week 12)

	Week 8	
 • Week 4 dose date 
Study day 29 if Week 4 dose is not received (either missed or IP discontinued prior to Week 4)
	
 • Week 8 dose date-1 
Study day 56 if Week 8 dose is not received (either missed or IP discontinued prior to Week 8)

	Week 12	
 • Week 8 dose date 
Study day 57 if Week 8 dose is not received (either missed or IP discontinued prior to Week 8)
	
 • Week 12 IP dose date-1 • If Week 12 dose is not received (either missed or IP discontinued prior to Week 12) 
 ○ MIN (Study day 84, EOS) if Week 8 dose is not received ○ MIN (Week 8 dose date + 27, EOS) if week 8 dose is

			received
--	--	--	----------

Study Visit

Since the actual visit for a subject may not exactly coincide with their targeted visit date, the actual visit date is mapped to a study visit.

The next study day window will be utilized to define study visit for lab, vital signs, C-SSRS and some PROs collected during office visits [REDACTED] before dose is administered [REDACTED]

Table 3 Study Visit Windows

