5.1.1 Study drug

Date of first study drug administration (Day 1)

Day 1 is defined as the first day of administration of randomized study drug (AMG334 or matching placebo). All other days will be labeled relative to Day 1. If subject will not be dosed at Day 1, the Study Day 1 is defined as day of randomization.

Date of last study drug administration

The date of last dose of randomized study drug is simply the day of the last dose.

5.1.2 eDiary data

The eDiary includes the following clinical outcome assessments:

- Incidence of headache (ie, migraine with or without aura or non-migraine headache)
- Time of onset of headache
- Time of resolution of headache
- Pain severity per headache
- Symptoms (eg, nausea, vomiting, photophobia, phonophobia)
- Presence of aura
- Use of acute medication during aura or to treat headache

As well as, patient-reported outcomes (PROs) measures of MPFID, [REDACTED]

Missing eDiary data in the calculation of monthly measurements about subjects' migraine and non-migraine headaches will be handled using the following method:

1. For monthly intervals with ≥ 14 days of eDiary days (including retrospective eDiary days) in each interval:

a) Monthly frequency measurements (including migraine days, headache days, [REDACTED] acute medication use, acute migraine specific medication use etc.) will be prorated to 28-day equivalents. Prorated result does not need to be rounded.

b) [REDACTED] impact on everyday activities scores as measured by MPFID will be calculated as the average of observed scores

2. For monthly intervals with < 14 days of eDiary use (including retrospective eDiary days), all monthly measurement will be set as missing and will be handled as described in [Section 5.1.6](#).

Table 8 Rules for handling missing and incomplete eDiary data

Monthly Endpoint	Condition	Proration Method (does not need to be rounded)
Monthly frequency measurements (including migraine days, headache days, [REDACTED] hours of migraine headaches, acute headache medication treatment days, acute migraine-specific medication treatment days)	If diary days in entire baseline or interval post baseline ≥ 14 (including retrospective eDiary days), then do proration; Else monthly measurement is set to missing [diary days is a day with all headache related questions completed retrospectively or not]	Number of observed migraine days * 28/ Number of information days in interval [information day is a diary day or headache day]

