5.5 Rule of exclusion criteria of analysis sets

The protocol deviations during screening, baseline and treatment periods are defined below (Table 10). The deviation ID, deviation code and it's corresponding text description are

explained in Table 9. Patients exclusion based on protocol deviations and non- protocol deviations criteria are in Table 11.

Table 8 Deviation Codes Description

Deviation code	Text description	Deviation ID
1	SELECTION CRITERIA NOT MET	INCLXX ; EXCLXX
2	PATIENT NOT WITHDRAWN AS PER PROTOCOL	WITHXX
3	PROHIBITED CONCOMITANT MEDICATION	COMDXX
4	TREATMENT DEVIATION	TRTXX
998	OTHER	OTHXX

Table 9 Protocol Deviations

Deviation ID	Description of Deviation
Scr INCL01	Informed consent not signed.
Scr INCL02	Adults <18 to >65 years of age
Scr INCL03	Documented history of migraine (with or without aura) for less 12 months prior to screening according to the International Classification of Headache Disorders-3rd Edition (ICHD-3)
Scr INCL04	< 4 or ≥15 days per month (in at least two separate attacks) of migraine symptoms (based on ICHD-3 criteria) on average across the 3 months prior to screening based on retrospective reporting
Scr INCL05	≥15 days per month of headache symptoms (ie migraine and non-migraine)
Scr INCL06	Not failed 2 to 4 prior migraine prophylaxis treatments out of the following: 
 Propranolol/metoprolol, topiramate, flunarizine, valproate/divalproex, amitriptyline, venlafaxine, lisinopril, candesartan, locally approved products (e.g. oxeterone or pizotifen)
Scr INCL07	Failed one and failed Or not be suitable for a second of the following: Propranolol or Metoprolol, Topiramate, Flunarizine
Scr INCL08	Failed or not be suitable for Valproate or Divalproex
Bln INCL09	Migraine frequency interval out of 4 to 14 migraine days during the Baseline Epoch, confirmed by the eDiary
Bln INCL10	<80% eDiary compliance during the Baseline Epoch
Scr EXCL01	To be older than 50 years of age at migraine onset
Scr EXCL02	To be unable to differentiate migraine from other headaches
Scr EXCL03	History of cluster headache or hemiplegic migraine headache

Deviation ID	Description of Deviation
Scr EXCL04	Failed more than 4 prior migraine prophylaxis treatments out of the following: Propranolol/metoprolol, topiramate, flunarizine, valproate/divalproex, amitriptyline, venlafaxine, lisinopril, candesartan, locally approved products (e.g. oxeterone or pizotifen)

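### SAP 2.4.1 understates eDiary compliance for complete diaries in dosing intervals shorter than 28 days, because the denominator is held at 28

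*SAP*

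**What the plan says.** SAP 2.4.1 defines monthly eDiary compliance in two branches. For an interval of 28 days or fewer it is "Number of observed eDairy days at baseline or between IP doses/ 28)*100" percent. The second branch applies "if Number of actual days in Baseline epoch or between IP doses interval > 28" and divides by the actual days in the interval. Both branches cover the Baseline Epoch and the intervals between doses.

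Interval lengths follow from two other places. Protocol 5.5.4 sets the dosing window: "The study drug administration date should be in 4 week increments (+/- 5 days) from the first dose of study drug". SAP 2.1.1, Table 2, ends each monthly interval on the day before the next dose (for the first interval, "Week 4 dose date-1"), so an interval is as long as the gap between two dose dates.

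The only compliance cut-off in either document is 80%, and it belongs to baseline. It is inclusion criterion 10 in Protocol 4.1 and deviation INCL10 in SAP 5.5, worded "<80% eDiary compliance during the Baseline Epoch".

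A separate rule decides whether a month's efficacy value exists. SAP 5.1.2 prorates to 28 days "For monthly intervals with ≥ 14 days of eDiary days (including retrospective eDiary days) in each interval" and sets the month to missing otherwise.

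**The concern.** A compliance percentage should compare the entries made with the entries that could have been made. In a 23-day interval only 23 daily entries are possible, yet the SAP divides by 28. In a 33-day interval it divides by 33. The two branches thus treat short and long intervals differently, and the discrepancy can only lower the score.

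The SAP recognises elsewhere that intervals vary in length: the migraine-day derivation in 5.1.2 divides by the information days in the interval. The compliance formula does not follow that logic for short intervals.

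What is at stake is the accuracy of a reported summary. A reader of the study report would use the compliance table to judge how completely the diary was kept. For patients dosed early but within the window, that table would mix diary behaviour with visit timing.

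**Working it through.** The documents give no compliance figure to reproduce, so the check applies the SAP formula directly.

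**Inputs**
- Formula and the 28-day switch: SAP 2.4.1.
- Window of 5 days either side of 4-week points counted from the first dose: Protocol 5.5.4.
- Interval length equals the gap between dose dates: SAP 2.1.1, Table 2.

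**Step 1: in-window interval lengths**
- Day 1 to Week 4: 28 − 5 = 23 days up to 28 + 5 = 33 days.
- Week 4 to Week 8: both ends can move. Shortest: (56 − 5) − (28 + 5) = 18 days. Longest: (56 + 5) − (28 − 5) = 38 days.
- Week 8 to Week 12, when a Week 12 dose is given: also 18 to 38 days.

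**Step 2: score for a patient with an entry every day**

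| Interval (days) | SAP formula | Entries / actual days |
|---|---|---|
| 28 or more | 100% | 100% |
| 27 | 27/28 = 96.4% | 100% |
| 26 | 26/28 = 92.9% | 100% |
| 25 | 25/28 = 89.3% | 100% |
| 24 | 24/28 = 85.7% | 100% |
| 23 | 23/28 = 82.1% | 100% |
| 22 | 22/28 = 78.6% | 100% |
| 18 | 18/28 = 64.3% | 100% |

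**Step 3: the asymmetry, with two missed days each time**
- 23-day interval: 21/28 = 75.0% under the SAP, against 21/23 = 91.3% on actual days.
- 28-day interval: 26/28 = 92.9% either way.
- 33-day interval: 31/33 = 93.9% either way.

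**Step 4: how many in-window schedules are touched**

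With whole-day offsets from −5 to +5 at both Week 4 and Week 8 there are 11 × 11 = 121 combinations. The interval is under 28 days when the Week 8 offset is smaller than the Week 4 offset: (121 − 11)/2 = 55 combinations. It is 22 days or fewer, so that a complete diary scores below 80%, when the Week 4 offset exceeds the Week 8 offset by 6 or more: 5 + 4 + 3 + 2 + 1 = 15 combinations. These count possible schedules and are not frequencies; the documents do not say how often visits fall early or late.

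**Step 5: baseline, conditional on assumptions**

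Suppose that this formula decided INCL10 and that the Baseline Epoch ran a little short. Then 22 entries in 27 days would score 22/28 = 78.6%, below 80%, against 22/27 = 81.5% on actual days. Both suppositions are assumptions.

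**The case against.** The strongest defence is that the rule is a minimum denominator. It equals entries divided by the larger of 28 and the actual days, which fits the 28-day normalised month used for efficacy. It also protects against a real distortion. SAP Table 2 can end the Week 12 interval at end of study when no Week 12 dose is given. If compliance follows those intervals, a patient who leaves ten days in with ten entries would score 10/10 = 100% on actual days, for a month that SAP 5.1.2 sets to missing. Under the present rule the score is 10/28 = 35.7%. This stands, and it rules out using actual days everywhere. It does not justify the rule for an interval closed by the next administered dose, where no planned days were lost. The SAP's change history says that the formula was updated for clarification, but no reason is given for the floor of 28.

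Three stronger inferences are tempting, and the documents support none of them.

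- *Diligent patients will be classed as non-compliant.* The SAP reports a percentage and has no post-baseline category or cut-off. One early dose after an on-time dose still gives at least 82.1%. With complete entries, a score below 80% needs a late dose followed by an early one.
- *False INCL10 deviations will arise.* The dosing window is counted from the first dose and does not set the length of the Baseline Epoch, which is planned at four weeks. SAP 2.11 has the investigator confirm eligibility from the eDiary before randomization, and nothing ties that check to the formula in 2.4.1. SAP 5.5 also lists no protocol deviation that removes a patient from any analysis set.
- *The primary endpoint is poorly supported.* Whether a month counts depends on the 14-day count, and its value on proration by information days. A complete 18-day interval qualifies and is prorated on 18 days, whatever its compliance score.

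**Conclusion.** The point holds as a defect in a descriptive measure. For complete diaries in in-window intervals under 28 days, the understatement runs from 3.6 percentage points at 27 days (100 − 96.4) to 17.9 at 23 days (100 − 82.1), the worst case for month 1. It reaches 35.7 at 18 days (100 − 64.3), the worst case for later intervals. It never runs the other way.

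The size in the study report depends on how often intervals fall short of 28 days, which the documents do not give. Protocol section 6 asks for visits as close to the designated day as possible, so the extreme cases may be rare. The calculation assumes that compliance intervals follow SAP Table 2.

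The primary and secondary efficacy results and the analysis sets do not depend on this percentage. Any effect on the baseline 80% criterion is conditional on both assumptions in Step 5. The change is minor but worth making.

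**What to change.** In SAP 2.4.1, split the formula by how the interval ended instead of by whether it exceeds 28 days:

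- For the Baseline Epoch and for intervals bounded by two administered doses: observed eDiary days / actual days in the interval × 100%.
- For intervals cut short by early withdrawal or end of study: keep the 28-day planned length as the denominator, so that lost days still count.

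Two short clarifications would complete it. State which case applies to intervals that Table 2 sets by study day after a missed dose. State also whether this formula is the one behind INCL10.

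The cost is a few lines of SAP text and two cases to code instead of one. Reported compliance will change slightly, upward, for patients with short completed intervals. No efficacy derivation needs to change.

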2.4.2 Rescue medication

Patients can continue to use “best supportive care”. This can include both pharmacologic interventions (ie, abortive treatments for acute attacks) and non-pharmacologic interventions (eg, biofeedback, psychotherapy, acupuncture or other locally accepted and endorsed interventions for migraine).

Site staff will pre-specify the name, dose strength, and route of administration of the patient’s acute headache (rescue) medications in the patient’s eDiary. If the patient takes an acute headache medication during aura or to treat a migraine or non-migraine headache, they will select one of the pre-specified medications (or “other” medication) and enter the date of administration, the number of times the medication was taken on that date and number of units taken.

Use of rescue medication must be recorded in the eDiary. Relevant non-drug therapies as part of “best supportive care” use should also be recorded in the eCRF.

2.4.3 Prior, concomitant and post therapies

The number and percentage of participants receiving rescue medications, prior best supportive care non-drug therapies and concomitant medication will be summarized by primary SOC, PT (according to the latest World Health Organization drug dictionary (WHO-DD) at the time of database lock, including Anatomical Therapeutic Chemical (ATC) classification code) and treatment arm.

The number and percentage of participants taking any prohibited or restricted treatment will also be summarized for SAF.

